### **11.6.8 Columbia-Suicide Severity Rating Scale (C-SSRS)**

The Columbia-Suicide Severity Rating Scale (C-SSRS) scale is composed of 11 items answered Yes or No. The C-SSRS also includes a suicidal ideation intensity rating from 1 (least severe) to 5 (most severe).

Results of the C-SSRS will be provided in data listings only.

## 13 Appendix 1 Glossary of Abbreviations

Glossary of Abbreviations:	
AE	Adverse event
ANCOVA	Analysis of covariance
ASP	Average sleep propensity
BLQ	Below the Quantifiable Limit
bpm	Beat per minutes
CGI-S	Clinical Global Impression of Severity
CI	Confidence Interval
COVID-19	Coronavirus Disease 2019
CRF	Case report form
C-SSRS	Columbia-Suicide Severity Rating Scale
CTG	Cytosine-thymine-guanine
CYP	Cytochrome P450
DBT	Double-Blind Treatment
DM1	Myotonic dystrophy type 1
DSS	Daytime Sleepiness Scale
ECG	Electrocardiogram
eCRF	Electronic case report form
EDS	Excessive daytime sleepiness
EOT	End of Treatment
ESS	Epworth Sleepiness Scale
ET	Early Termination
FDA	Food and Drug Administration
FSS	Fatigue Severity Scale
GCP	Good Clinical Practice
H 1	Histamine 1
ICH	International Council for Harmonisation
IP	Investigational product
IRT	Interactive Response Technology
LOE	Lack of efficacy
LS	Least square
MDHI	Myotonic Dystrophy Health Index
MedDRA	Medical Dictionary for Regulatory Activities

Glossary of Abbreviations:	
mITT	Modified Intent-to-Treat
MMRM	Mixed effect model repeated measures
MSL	Mean sleep latency
MWT	Maintenance of Wakefulness Test
NIH	National Institutes of Health
OLE	Open-Label Extension
PD	Protocol deviations
PGI-S	Patient Global Impression of Severity
PK	Pharmacokinetic(s)
PT	Preferred term
QTcF	QT interval corrected for heart rate based on Fridericia's formula
RT	Reaction time
SAE	Serious adverse event
SAP	Statistical analysis plan
SART	Sustained Attention to Response Task
SD	Standard deviation
SE	Standard error
SI	International System of Units
SoA	Schedule of Assessment
SOC	System organ class
TEAE	Treatment-emergent adverse event
WHO	World Health Organization

## 14 Appendix 5 Adverse Event Start/Stop Date Imputation

### Imputation Rules for Partial Dates (D = day, M = month, Y = year)

Parameter	Missing	Additional Conditions	Imputation
Start date for AEs	D	M and Y same as M and Y of first dose of study drug	Date of first dose of study drug
		M and/or Y not same as date of first dose of study drug	First day of month
	D and M	Y same as Y of first dose of study drug	Date of first dose of study drug
		Y prior to Y of first dose of study drug but same as Y of screening date	Date of screening date
	D, M, Y	None - date completely missing	Date of first dose of study drug
Stop date for AEs	D	M and Y same as M and Y of last dose of study drug	Date of last dose of study drug
		M and/or Y not same as date of last dose of study drug	Use last day of month
	D and M	Y same as Y of last dose of study drug	Date of last dose of study drug
		Y not same as Y of last dose of study drug	Use Dec 31
	D, M, Y	None - date completely missing	No imputation, but assume ongoing

Note: In all cases, if an estimated start date is after a complete stop date, use the first day of the stop date month.

Similarly, if the estimated stop date is before a complete or imputed start date, use the last day of the start day month.

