## 9.2 Study Day Windows

For each patient there will be a screening period, a Double-Blind Treatment Phase, and an optional OLE Phase.

The study day for data collected after the first dose of study drug will be calculated as visit/assessment date – first dose date + 1. For data collected prior to first dose, the study day will be calculated as visit/assessment date – first dose date. The first dose date refers to the date the study drug was taken for the first time, i.e., at the beginning of the Double-Blind Treatment Phase.

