## 9.4 Double-Blind and OLE Analyses Reporting

The data collected for the Double-Blind Treatment Phase and the OLE Phase are included in the same database.

A data cut will be performed at the end of the Double-Blind Treatment Phase and another one will be performed at the end of the OLE Phase. The date of first dose in the OLE Phase will be used to determine if a patient entered the OLE Phase. A data cut-off will be applied to the datasets and only data related to the Double-Blind Treatment Phase will be reported:

- Baseline and baseline characteristics.
- Visits performed in the Double-Blind Treatment Phase, up to and including Visit 5 (Week 11) for patients who entered the OLE Phase, and up to the safety follow-up visits for patients who opt out of the OLE Phase.
- For patients who entered the OLE Phase, any adverse event (AE) or medication that started up to and including the last dose of study drug in the Double-Blind Treatment Phase. For this patient group a (any AE or medication that started after and up to 30 days after the last dose of study drug in the Double-Blind Treatment Phase will be reported in separate listings, i.e., they will be excluded from the Double-Blind Treatment Phase summary tables).
- For patients who opt out of the OLE Phase, all AEs and medications reported through the final 30-day safety follow-up telephone contact will be reported as part of the Double-Blind Treatment Phase.

The date of first dose in the OLE Phase will be kept in the datasets to determine if the patient has entered the OLE Phase.

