All AEs will be coded using MedDRA; the version used will be included in the tables and listings footnotes. The TEAEs will also be summarized by system organ class (SOC) and preferred term (PT), by severity and relationship to study treatment.

The TEAE summary tables will be sorted by SOC and PT. SOC's will be displayed in descending order of overall frequency in the pooled pitolisant group and then alphabetically. PTs will be displayed in descending order of overall frequency and then alphabetically within SOC. A patient with 2 or more events within the same PT of summarization will be counted only once in that level using the most severe incident or most related incident. Percentages will be based on the number of patients in the safety population. The following summaries by SOC and PT will be provided:

- TEAE
- Treatment-related TEAE
- TEAE by maximum severity
- Serious TEAE
- Treatment-related serious TEAE
- TEAE leading to discontinuation of IP
- TEAE leading to interruption of IP
- TEAE leading to death

Finally, a summary of all AEs and all SAEs by SOC and PT will be provided.

All AEs will be presented in a data listing. Separate data listings will be generated for treatment related AEs, SAEs, and AEs leading to study discontinuation.

For patients who opt to continue in the OLE Phase of the study, only AEs started on or before the last dose of the Double-Blind Treatment Phase will be included in the summaries for the Double-Blind Treatment Phase. AEs started after the last dose of treatment and up to 30 days after the last dose of treatment in the Double-Blind Treatment Phase will be included in a separate listing and summarized in the OLE Phase reporting.

For clinicaltrials.gov and other registries, the following will be produced in XML format.

1. All-Cause Mortality: \*§ A table of *all* anticipated and unanticipated deaths due to any cause, with the number and frequency of such events by arm or comparison group of the clinical study.
2. Serious Treatment-Emergent Adverse Events: \* A table of *all* serious adverse events, grouped by System Organ Class, with the number and frequency of such events by arm or comparison group of the clinical study.

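### AE start-date imputation refers only to the first double-blind dose, so some open-label events with partial dates are dated into the double-blind phase

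*SAP*

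**What the plan says.** **Imputation (SAP Appendix 5, AE start dates).** The only anchors are the first dose of study drug and, for an earlier year, the screening date.

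- Day missing, first-dose month: date of first dose. Day missing, "M and/or Y not same as date of first dose of study drug": first day of the recorded month.
- Day and month missing, "Y same as Y of first dose of study drug": date of first dose. Day and month missing, "Y prior to Y of first dose of study drug but same as Y of screening date": screening date. A year after the first-dose year is not mentioned.
- "None - date completely missing": date of first dose.

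The note under the table covers only an estimated start that falls after a complete stop date, and the converse for estimated stop dates.

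**Meaning of first dose (SAP 9.2).** "The first dose date refers to the date the study drug was taken for the first time, i.e., at the beginning of the Double-Blind" phase. Where the first open-label dose is meant, SAP 9.4 names it separately.

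**Assignment to phase.** For OLE entrants, the double-blind report takes "any adverse event (AE) or medication that started up to and including the last dose of study drug in the Double-Blind Treatment Phase" (SAP 9.4). SAP 11.6.1 repeats this for the AE tables: "only AEs started on or before the last dose of the Double-Blind Treatment Phase will be included in the summaries". An event is treatment-emergent in the OLE if it starts on or after the first OLE dose (SAP 11.6.1). Both phases share one database (SAP 9.4).

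**The concern.** The imputation table is written as if the trial had one treatment phase. In that setting, pulling an uncertain start back to the first dose is conservative, because the event is then counted as treatment-emergent. Here there are two phases, every OLE patient takes pitolisant whatever the randomized arm, and the start date decides which phase an event belongs to. An event that began on open-label pitolisant can therefore be given a start before the first OLE dose. It would then be eligible for the randomized by-arm tables, including the placebo column, and would fail the start-date test for the OLE table. Safety is part of the primary objective, and the arms are small enough for one patient to show.

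**Working it through.** The documents give no figure on this point, so there is nothing to reproduce. The check applies the Appendix 5 rules to every open-label day.

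**Inputs.** OLE from Day 78 to Day 459 (SAP 8.1 and Table 2): 459 − 78 + 1 = 382 days. OLE titration, Days 78 to 98: 21 days. About 30 patients randomized 1:1:1 (SAP 8.1): about 10 per arm.

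**Assumptions.** Day 1 is uniform over a 365-day year, the last double-blind dose is Day 77, the first OLE dose is Day 78, and event days are uniform over the OLE. An event counts as moved if its imputed start is on or before Day 77.

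**(a) Completely missing date.** Always set to Day 1, so 100% of OLE days are affected.

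**(b) Day and month missing.** Let R be the number of days from Day 1 to 31 December inclusive, uniform on 1 to 365. OLE days in the first-dose year = max(0, R − 77).
- Mean = (1 + 2 + … + 288)/365 = (288 × 289/2)/365 = 41,616/365 = 114.0 days.
- Share moved to Day 1 = 114.0/382 = 29.8%. The other 70.2% fall in a later year, where there is no rule.
- Titration days only: (1 + … + 21 + 267 × 21)/(365 × 21) = 5,838/7,665 = 76.2%.

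**(c) Day missing.** Only the part of the switch month from the first OLE dose onward is affected, and nothing is affected if the OLE starts on the 1st.
- Exposed days, summed over all starting days: 465 for a 31-day month, 435 for a 30-day month, 378 for February. Mean = (7 × 465 + 4 × 435 + 378)/365 = 5,373/365 = 14.7 days.
- Share = 14.7/382 = 3.9%. Day-only gaps in later months stay in the OLE.
- Titration days only, capping exposed days at 21: (7 × 420 + 4 × 399 + 357)/(365 × 21) = 4,893/7,665 = 63.8%.

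**Example.** Day 1 is 1 Feb 2022, the last double-blind dose is 18 Apr, and the OLE starts on 19 Apr.

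| True start | Recorded | Imputed start | Phase by start date |
|---|---|---|---|
| 15 Oct 2022 (Day 257) | 2022 | 1 Feb 2022 | double-blind |
| 25 Apr 2022 (Day 84) | Apr 2022 | 1 Apr 2022 | double-blind |
| 10 Jun 2022 (Day 130) | Jun 2022 | 1 Jun 2022 | OLE (correct) |

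**Missing row.** With Day 1 on 1 Oct 2022, an event on 10 Feb 2023 recorded as 2023 has no imputed start at all. The medication table (SAP Appendix 2) covers this case by using 1 January of the recorded year.

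**Effect on a rate.** One patient wrongly counted in an arm of 10 adds 1/10 = 10 percentage points.

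**Timing of the data cut.** The double-blind analysis may be run while patients are still in the OLE (Protocol 9.4.2.1). Events recorded by then can enter the by-arm tables. Events recorded later but imputed to the double-blind phase would miss the tables already produced and still fail the OLE start-date rule. An earlier cut also raises the share in (b): 63.7% for OLE days through Day 189.

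**The case against.** **Scope.** A reader might infer that open-label events with partial dates are generally pulled back. They are not. About 96% of OLE days are safe under the day-only rule, and about 70% under the year-only rule are left without a rule rather than moved. Not every day-missing event in the switch month is misplaced either, because some did begin before the switch. For a 30-day month with uniform dates, the misplaced share of all such events is (1 + … + 29)/900 = 435/900 = 48%. This objection stands, and the point is limited to the three cases above.

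**Direction.** A reader might also infer that the rules favour pitolisant by loading drug events onto placebo. The documents do not support that. With 1:1:1 allocation, about two thirds of OLE entrants would be expected to come from the pitolisant arms, and their misplaced events raise the pitolisant rates. If OLE event rates are similar by former arm, the expected difference does not shift. A net bias would need former placebo patients to have more events on open-label drug, which is plausible but not shown. What remains is that every arm's rate can be contaminated.

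**Frequency.** AEs are reviewed at Visit 5 (Day 77) and then on Days 85, 92 and 99, so very incomplete dates should be uncommon near the switch, although later contacts are about 90 days apart. The documents give no count of partial dates, so the frequency cannot be bounded.

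**Text.** SAP 11.6.1 does not cite Appendix 5, whereas SAP 11.3.1 does cite Appendix 2 for medications. SAP 9.4 also limits the double-blind report to data related to that phase. Using imputed dates for phase assignment is therefore an inference. No other rule is given for a partial start date, so the gap remains.

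**Importance.** The study is exploratory, no formal safety statistics are planned, and all AEs are listed. This lowers the severity but does not make the derivation right.

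**Conclusion.** Wrong as written, low severity. Appendix 5 combined with the phase rules in SAP 9.4 and 11.6.1 dates some open-label events into the double-blind phase and removes them from the OLE treatment-emergent table. The later-year gap is a separate omission in the same table. Only OLE entrants are affected. The 100% figure follows from the rule itself. The 29.8%, 3.9%, 63.8% and 76.2% figures are shares of OLE days under uniform dates, not forecasts of how many events will be misplaced. The 10-point shift is the effect of one patient, not an estimate of bias.

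**What to change.** In SAP Appendix 5, for patients who enter the OLE:

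1. Add a row for day and month missing in a year after the first-dose year: 1 January of that year, as in Appendix 2.
2. If the event was first recorded at a contact after the first OLE dose, and neither the known date parts nor a stop date places it before that dose, set the start to the later of the rule's date and the first OLE dose date.
3. Otherwise apply the existing rules.

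In the example above, the two misplaced events would both be dated 19 Apr 2022. Step 2 is also needed for the new row. With Day 1 on 1 Dec 2022 the first OLE dose is 16 Feb 2023, so an event recorded only as 2023 would be set to 1 Jan 2023, inside the double-blind phase, without the floor.

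**Cost.** A few rows in a derivation table and one listing, with no new data collection if the contact at which each AE was first recorded can be taken from the database. The documents do not confirm that it can, so this should be checked before lock.

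**Downside.** A double-blind event first mentioned after the switch, with only a partial date, may be placed in the OLE. A listing of the AEs whose phase depends on imputation would make both kinds of error visible.

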## 15 Appendix 2 Prior and Concomitant Medication Start/Stop Date Imputation

### Imputation Rules for Partial Dates (D = day, M = month, Y = year)

Parameter	Missing	Additional Conditions	Imputation
Start date for con meds	D only	M and Y same as M and Y of first dose of study drug	Date of first dose of study drug
		M and/or Y not same as date of first dose of study drug	First day of month
	M and D	Y same as Y of first dose of study drug	Date of first dose of study drug
		Y not same as Y of first dose of study drug	Use Jan 01 of Y
	M, D, and Y	None - date completely missing	Day prior to date of first dose of study drug
Stop date for con meds	D only	M and Y same as M and Y of last dose of study drug	Date of last dose of study drug
		M and/or Y not same as date of last dose of study drug	Last day of month
	M and D	Y same as Y of last dose of study drug	Date of last dose of study drug
		Y not same as Y of last dose of study drug	Use Dec 31 of Y
	M, D, and Y	None - date completely missing and NOT ongoing	Date of last dose of study drug

Note: In all cases, if an estimated start date is after a complete stop date, use the first day of the stop date month.

Similarly, if the estimated stop date is before a complete or imputed start date, use the last day of the start day month.

## 16 Appendix 3 Example of Prohibited Medications

Examples of strong CYP2D6 Inhibitors, strong CYP3A4 Inducers, Medications that prolongQT Interval, And Centrally Acting H1R Antagonists.

Medicaiton Type	Example
Strong CYP2D6 inhibitors	paroxetine, fluoxetine, bupropion, quinidine, terbinafine
Strong CYP3A4 inducers	rifampin, carbamazepine, phenytoin, apalutamide, St John's wort, enzalutamide, mitotane
Medications that prolong QT interval	Class 1A antiarrhythmics : quinidine, procainamide, disopyramide; Class 3 antiarrhythmics : amiodarone, sotalol; dofetilide Antipsychotics : ziprasidone, chlorpromazine, thioridazine, haloperidol Antibiotics : moxifloxacin, ciprofloxacin, erythromycin, ketoconazole
Centrally acting H 1 receptor antagonists (sedating or lipophilic H 1 R antagonists)	pheniramine maleate, diphenhydramine, promethazine (anti-histamines) imipramine, clomipramine, mirtazapine (tri or tetracyclic antidepressants).

CYP = cytochrome P450; H1R = histamine 1 receptor

---

## 17 Appendix 4 SAS Sample Code

Below are some examples of code for inferential statistics described in the SAP.

### ANCOVA:

```
proc mixed data=datain;  
  class trtpn wkprag;  
  model chg = base trtpn wkprag / solution;  
  lsmeans trtpn / cl stderr pdiff cov;  
  estimate 'pooled vs placeco' 0.5 0.5 -1 / cl;  
  ods output diffs = lsdiffs lsmeans = lsm solutionf = parms;  
run;
```

### MMRM:

```
proc mixed data=datain;  
  class subjid trtpn avisitn wkprag;  
  model chg = base trtpn avisitn trtpn*avisitn wkprag / ddfm=KenwardRoger;  
  repeated visit / subject = subjid type = UN;  
  lsmeans trtpn / cl stderr pdiff cov;  
  estimate 'pooled vs placeco' 0.5 0.5 -1 / cl;  
  ods output diffs = lsdiffs lsmeans = lsm solutionf = parms;  
run;
```

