### 11.4.1 Double-Blind Treatment Phase

All efficacy analyses will be performed on the mITT Population. The analysis approaches for the efficacy endpoints at Visit 5 are detailed in [Table 7](#). Similar analyses (where applicable) for efficacy endpoints collected at Visit 4 will be conducted as well.

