**Table 7: Double-Blind Inferential Analyses Strategy**

Endpoint	Primary/ Secondary/ Exploratory	Inference model	Comparisons of interest
CFB in DSS score at Week 11 (Visit 5)	Primary	MMRM	Higher dose vs. Placebo; Lower dose vs. Placebo; Pooled active vs. Placebo
CFB in ESS score at Week 11 (Visit 5)	Secondary	MMRM	Higher dose vs. Placebo; Lower dose vs. Placebo; Pooled active vs. Placebo
CFB in FSS score at Week 11 (Visit 5)	Secondary	MMRM	Higher dose vs. Placebo; Lower dose vs. Placebo; Pooled active vs. Placebo
CFB in Cogstate Detection Test score at Week 11 (Visit 5)	Secondary	ANCOVA	Higher dose vs. Placebo; Lower dose vs. Placebo; Pooled active vs. Placebo
CFB in Cogstate Identification Test score at Week 11 (Visit 5)	Secondary	ANCOVA	Higher dose vs. Placebo; Lower dose vs. Placebo; Pooled active vs. Placebo
CFB in Cogstate One Back Test score at Week 11 (Visit 5)	Secondary	ANCOVA	Higher dose vs. Placebo; Lower dose vs. Placebo; Pooled active vs. Placebo
CFB in MDHI total Score at Week 11 (Visit 5)	Secondary	MMRM	Higher dose vs. Placebo; Lower dose vs. Placebo; Pooled active vs. Placebo
CFB in CGI-S score at Week 11 (Visit 5)	Secondary	MMRM	Higher dose vs. Placebo; Lower dose vs. Placebo; Pooled active vs. Placebo
CFB in PGI-S score at Week 11 (Visit 5)	Secondary	MMRM	Higher dose vs. Placebo; Lower dose vs. Placebo; Pooled active vs. Placebo
CFB in SART go score at Week 11 (Visit 5)	Secondary	Kruskal-Wallis	Higher dose vs. Placebo; Lower dose vs. Placebo; Pooled active vs. Placebo
CFB in SART no-go score at Week 11 (Visit 5)	Secondary	Kruskal-Wallis	Higher dose vs. Placebo; Lower dose vs. Placebo; Pooled active vs. Placebo
CFB in SART total score at Week 11 (Visit 5)	Secondary	Kruskal-Wallis	Higher dose vs. Placebo; Lower dose vs. Placebo; Pooled active vs. Placebo

Endpoint	Primary/ Secondary/ Exploratory	Inference model	Comparisons of interest
CFB in MSL at Week 11 (Visit 5)	Exploratory	ANCOVA	Higher dose vs. Placebo; Lower dose vs. Placebo; Pooled active vs. Placebo

Abbreviations: ANCOVA = Analysis of Covariance; CGI-S = Clinical Global Impression of Severity; CFB = Change from Baseline; DSS = Daytime Sleepiness Scale; ESS = Epworth Sleepiness Scale; FSS = Fatigue Severity Scale; MDHI = Myotonic Dystrophy Health Index; MSL = Mean Sleep Latency; PGI-S = Patient Global Impression of Severity.

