## 11.4.2 Primary Efficacy Analysis

### 11.4.2.1.1 Daytime Sleepiness Scale (DSS)

The DSS is a questionnaire in which patients are asked to assess five items with scores of never (0), seldom (1), often (2), and always (3). The DSS score is the sum of the answers to questions 1 to 4 plus the reversed score to question 5 (i.e., minus the score for question 5). If at least one question is not answered, the score will be set to missing.

The DSS score can vary from 0 to 15 and the higher the score, the higher the degree of sleepiness. The questionnaire was developed and validated in patients with DM1 in three subgroups: early adult-onset (onset of symptoms from 11-20 years old), adult (onset of symptoms from 21-40 years old) and mild (onset of symptoms at >40 years old). The instrument has demonstrated construct (factorial) validity ([Laberge et al 2004](#)), convergent and discriminant validity ([Laberge et al 2009](#); [Laberge and Dauvilliers 2010](#)) and responsiveness ([Laberge et al 2021](#)).

A descriptive summary of DSS (mean, SD, median, minimum, maximum) for the absolute values and change from Baseline to Week 7 and to Week 11 will be presented by treatment group and for the active groups combined. If the termination visit occurs after the Week 7 Double-Blind visit, the early termination data will be windowed to Week 11 regardless of the discontinuation reason.

The change from Baseline to Week 11 will be analyzed using a Mixed Model Repeated Measures (MMRM) approach. Fixed effects will be included for treatment, visit, treatment\*visit interaction, baseline value, and stratification factor. An unstructured covariance structure will be utilized; in case of failure to converge, covariance structures TOEPH (Heterogeneous Toeplitz), ARH(1) (Heterogeneous auto-regressive 1), and VC (Variance Components) will be tested in the order specified. Least Square means, standard errors, and the LS mean differences (each treatment versus placebo and the pooled active groups versus placebo) at each visit will be reported. All estimates will be generated from a single model, i.e., the pooled active estimates will be created via model contrasts.

If there is more than a 10% difference between the stratification factor recorded in IRT versus the stratification factor derived from the prior and concomitant in the EDC, the MMRM analysis will be repeated using the stratification factor reported in IRT.

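### The SAP's example MMRM code does not produce the Week 11 (Visit 5) and by-visit differences that the SAP text requires; repaired only for syntax, it averages Visits 4 and 5

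*SAP*

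**What the plan says.** **The text.** SAP 11.4.1 states that "The analysis approaches for the efficacy endpoints at Visit 5 are detailed in" Table 7, and adds that similar analyses will be done at Visit 4 where the endpoint is collected there. Table 7 lists DSS at Week 11 (Visit 5) as the primary endpoint, with MMRM as the model and three comparisons: higher dose, lower dose and pooled active, each versus placebo. SAP 11.4.2.1.1 then says that "the LS mean differences (each treatment versus placebo and the pooled active groups versus placebo) at each visit will be reported". The same output is required for FSS (11.4.3.1.1), MDHI (11.4.3.1.5), ESS (11.4.3.1.6) and CGI-S (11.4.3.1.7), and for PGI-S by reference (11.4.3.1.8). That makes six MMRM endpoints.

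**The code.** Appendix 4 opens with "Below are some examples of code for inferential statistics described in the SAP". The MMRM example puts baseline, treatment, `avisitn`, treatment by `avisitn` and the wake-promoting stratum in the MODEL statement. Its post-fit requests are:

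- "lsmeans trtpn / cl stderr pdiff cov"
- "estimate 'pooled vs placeco' 0.5 0.5 -1 / cl"

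Its covariance line is "repeated visit / subject = subjid type = UN". The CLASS list contains `avisitn` but not `visit`.

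**The concern.** No line of the MMRM example asks for a result at Visit 5 or at Visit 4. There is no LSMEANS for treatment by visit, no slice, and no contrast with interaction coefficients.

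A programmer who starts from this example will first clear the two syntax faults. The code should then give clean, plausible output: one treatment difference per comparison, with no visit label to show that it is not the Week 11 result. Because the study is descriptive, the estimates and their standard errors are themselves the result, so their time point matters. The example is the only written implementation of the model for the primary endpoint and five secondary ones. It is also maintained text: the SAP change history records that version 2.0 added the stratification factor to the Appendix 4 code, in the same version that moved the primary analysis from ANCOVA to MMRM.

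**Working it through.** There is no planned figure to reproduce. The check is on what the code's linear contrasts estimate.

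**Inputs from the documents.** Three arms at 1:1:1 and about 30 patients (SAP 8.4). Two post-baseline visits with scheduled DSS: Day 49 (Visit 4, Week 7) and Day 77 (Visit 5, Week 11) (Protocol synopsis, Efficacy Assessments). Fixed effects as in SAP 11.4.2.1.1.

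**Assumed inputs.** 10 patients per arm, equal variances at the two visits, and between-visit correlation rho. The documents give neither correlations nor effect sizes by visit.

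**Step 1: does it run as printed?** PROC MIXED requires the REPEATED effect to be built from CLASS variables, and `visit` is not one. An ESTIMATE statement must name the effect its coefficients belong to, and this one names none. On those rules the code should stop with errors. SAS was not available, so this was not executed.

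**Step 2: what does it estimate after a syntax-only repair?** Change `visit` to `avisitn` and insert `trtpn` before the coefficients. Let D4 and D5 be a dose-minus-placebo difference at Visits 4 and 5. With treatment by visit in the model, LS means for `trtpn` alone weight the visit levels equally, so:

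- each dose versus placebo = 0.5 × D4 + 0.5 × D5.

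For the pooled ESTIMATE, coefficients given only for `trtpn` are spread equally over the visits. In the order lower V4, lower V5, higher V4, higher V5, placebo V4, placebo V5, the interaction weights become 0.25, 0.25, 0.25, 0.25, -0.5, -0.5. This is again the two-visit average.

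A generalized least squares fit on this design (covariance treated as known) gave a discrepancy of 0 from the average, for both the higher-dose and the pooled contrast, at rho 0.3, 0.6 and 0.8.

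**Step 3: how far can that be from Week 11?** If D4 = r × D5, the repaired code returns (1 + r)/2 times the Week 11 difference:

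| r (assumed) | Result / Week 11 difference |
|---|---|
| 0 | 0.50 |
| 0.5 | 0.75 |
| 0.75 | 0.875 |
| 1 | 1.00 |
| 1.25 | 1.125 |

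**Step 4: standard error.** With equal variances s² and complete data, Var(average) = (s² + s² + 2·rho·s²)/4 = s²(1 + rho)/2. The ratio to the Week 11 SE is therefore sqrt((1 + rho)/2):

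- rho 0.4: sqrt(0.70) = 0.84
- rho 0.6: sqrt(0.80) = 0.89
- rho 0.8: sqrt(0.90) = 0.95

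The generalized least squares fit with baseline and stratum gave 0.811, 0.898 and 0.950 at rho 0.3, 0.6 and 0.8, against 0.806, 0.894 and 0.949 from the formula.

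**Step 5: do by-visit contrasts recover the right quantity?** A pooled Visit 5 contrast needs `trtpn` 0.5, 0.5, -1 and interaction weights 0, 0.5, 0, 0.5, 0, -1. Within each arm the interaction weights sum to the treatment weight (0.5, 0.5, -1). Within each visit they sum to 0, so the visit main effect cancels and the contrast is estimable. The Visit 4 version (0.5, 0, 0.5, 0, -1, 0) passes the same test.

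**The case against.** The strongest reply is that this is sample code. Appendix 4 calls it examples, and the governing text is explicit and repeated for every MMRM endpoint. Protocol 9.1.2 makes the analyses descriptive, and SAP 11 plans no formal testing apart from SART. Code that should not run cannot silently produce a wrong table: someone must rewrite it, and the text tells them what to report. The LS means that Protocol 9.1.1 takes as its population-level summary come from the model in Protocol 9.4.2.1.1, not from Appendix 4, and the example's fixed effects agree with that model.

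All of this stands as a limit on severity. It does not remove the mismatch: the obvious repair clears the errors and still leaves the wrong request in place.

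Two stronger readings are tempting, and the documents do not support them.

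- A reader might infer that the planned primary estimand is wrong or that the result will be biased. The text names Week 11 correctly, and no effect sizes by visit are given, so neither the direction nor the size of any error can be stated.
- A reader might infer that DSS early-termination records will add a third visit level and make the LS means non-estimable. Table 5 puts Days 2 to 35 under Visit 3, the early-termination visit repeats the Visit 5 efficacy assessments (Protocol 7.2.5), and the DSS rule covers only later cases: "If the termination visit occurs after the Week 7 Double-Blind visit, the early termination data will be windowed to Week 11". But DSS is not scheduled at Visit 3, section 11.4.2.1.1 summarises only Weeks 7 and 11, and nothing says a Visit 3 level enters the model. The other endpoints also refer to the section 9.2 windows, so DSS cannot be singled out. No standard error can be attached to such a case either: with one record per cell, the Visit 3 variance could not be estimated.

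**Conclusion.** The mismatch is real and minor. The Appendix 4 MMRM example does not deliver the Week 11 or by-visit differences that the SAP text requires for DSS and five secondary endpoints. After a syntax-only repair it estimates the equal-weight mean of the Visit 4 and Visit 5 differences. That coincides with the Week 11 difference only when the two effects are equal, and even then its standard error differs from the Week 11 one.

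The averaging result follows from the model and the two scheduled visits. The standard-error ratios rest on assumed correlations, equal variances and complete data. The statement that the printed code should not run rests on PROC MIXED rules and was not tested. The planned analysis in the text is sound; only the example is out of line with it.

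**What to change.** Edit SAP Appendix 4.

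**MMRM example**

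1. Restrict the input to analysis Visits 4 and 5, the only visits 11.4.2.1.1 summarises, so that the coefficients below match the model.
2. Use `repeated avisitn / subject=subjid type=un`.
3. Replace the LSMEANS request with `lsmeans trtpn*avisitn / cl diff`. Report the within-visit differences, with Visit 5 as the primary time point.
4. State the level order (`trtpn` = lower, higher, placebo; `avisitn` = Visit 4, Visit 5) and give one pooled contrast per visit:
   - Visit 4: `trtpn 0.5 0.5 -1 trtpn*avisitn 0.5 0 0.5 0 -1 0`
   - Visit 5: `trtpn 0.5 0.5 -1 trtpn*avisitn 0 0.5 0 0.5 0 -1`
5. Save the ESTIMATE results through ODS OUTPUT, which the example does not do. Add SOLUTION to the MODEL statement, because `solutionf` is requested there without it.

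**ANCOVA example**

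Name the effect in the ESTIMATE statement: `trtpn 0.5 0.5 -1`. There is no visit term, so the averaging problem does not arise.

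**Cost.** A few lines in one appendix. The SAP's analysis text, data collection and patients are unaffected.
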